3.2 Efficacy

Outcome assessments will primarily be made at baseline, one, and three months post procedure for patients receiving either the active treatment or sham procedure. Clinical assessments of pain will be made at all clinic visits.

Primary outcome: **safety** as assessed from adverse event reporting and MRI evaluation

Primary efficacy outcome measure will compare the change of **WORST** pain experienced in 24 hours before and at 3 months following bilateral FUS medial thalamotomy versus sham procedures as determined from the 11-point numeric pain rating scale.

Secondary outcome measures will include other patient-reported outcomes including the Global Impression of Change and the Pain Domain from the PROMIS Inventory including items for intensity, quality, behavior and interference.

Imaging assessments will be obtained before and after treatment. The location and precision of the treatment, as well as the volume of the lesion, will be determined from pre- and posttreatment MRI at baseline, 1 day, 1 week, 1 month and 3 months. Functional imaging assessments with Dynamic 2-[¹⁸F] fluoro-2-deoxy-D-glucose Positron Emission Tomography (FDG PET) will be obtained at baseline and three months for each patient. Functional imaging will serve as an objective measure to correlate with clinical pain assessment.

A summary of outcome measures is listed:

Primary (efficacy) outcome: 11-point numeric pain rating scale NPRS (“worst” NPRS score over 24 hours). The change in pain rating from baseline to 3 months posttreatment will be determined and compared between treatment and control cohorts.

Secondary outcomes:

Patient-reported outcome measures:

- PROMIS scale v1.0 – Pain Intensity 3a
- PROMIS scale v2.0 – Neuropathic Pain Quality 5a
- PROMIS scale v2.0 – Nocioceptive Pain Quality 5a
- PROMIS scale v1.0 – Pain Behavior 7a
- PROMIS scale v1.0 – Pain Interference 8a
- Patient Global Impression of Change, 7 point

Functional imaging assessments:

- Dynamic FDG PET

4.0 HYPOTHESIS

Study hypothesis: For patients with treatment-refractory chronic trigeminal neuropathic pain, ExAblate Neuro can safely create lesions in the bilateral thalamic nuclei to reduce pain and provide functional benefits in daily activities.

4.1 The Hypotheses Tested

- For patients with treatment-refractory chronic trigeminal neuropathic pain, MR guided focused ultrasound can safely create lesions, bilaterally, in thalamic nuclei to reduce pain and provide functional benefits in daily activities.
- FUS under MRI-guidance and MRI-based thermometry can be safely delivered through an intact human skull with a low risk of transient adverse effects as evaluated during blinded follow-up of up to 3 months and an additional 3 months follow-up in open-label setting for those subjects who were initially randomized to Sham treatment.
- Pre-defined medial thalamic target volumes inside the brain can be precisely ablated, as demonstrated on post-treatment MRI.

4.2 Case Report Form Data

The study data will be collected electronically. This electronic data capture (EDC) system complies with the current guidance of 21 CFR Part 11, Electronic Records and Signatures.

5.0 DESCRIPTION OF PATIENT POPULATION

Subject Selection

The cohort of subjects with chronic trigeminal neuropathic pain should represent a relatively homogenous pain condition that can be quantitatively diagnosed and treated with a minimal number of confounding factors (e.g. mood disorders, secondary gain, and additional interventions). Subjects diagnosed with a painful cranial neuropathy that is deemed treatment-resistant will be eligible for this study. The principal investigator has a clinical practice of surgery for medication-refractory cranial neuralgias and neuropathies, and he has experience in the classification and diagnosis of these chronic trigeminal neuropathic pain syndromes.⁹⁸

Subjects will first be consented in the study, and then will receive the standard clinical, psychological, and imaging work-up as part of their study baseline requirements. A total of ten (10) subjects will be recruited from University of Virginia Health System in this feasibility study.

5.1 Subject Enrollment

- a) Subjects will be referred primarily from the Neurosurgery or Pain Management clinics at the University of Virginia. Information concerning preliminary eligibility for the study will initially be taken from the subject's case history. Subjects who appear to be eligible will be asked if they would like to participate in this study.
- b) Written informed consent will be obtained from each participating subject prior to collecting a subject history or other testing. The subject will be counseled concerning the research nature of this study, and the risks and possible benefits to participation. Participation is fully voluntary.

5.2 Inclusion Criteria

1. Men and women, between 18 and 75 years, inclusive
2. Subjects who are able and willing to give consent and able to attend all study visits
3. Severe chronic, trigeminal neuropathic pain of ≥ 6 months duration.
4. Severity is defined as: Worst NPRS score of ≥ 5 out of 10 at current visit and the subject reports having a similar level of pain for at least the past two months.
5. Pain is medication-refractory to adequate trials of at least 3 prescription medications commonly used for symptomatic relief of neuropathic pain with current adjunctive use of at least one medication. An adequate medication trial is defined as a therapeutic dose of each medication without sufficient effect.
6. Pain is treatment-resistant to at least one interventional therapies including injections, procedures, neuromodulation, and surgery. The interventions trialed depend on the disease and are more specifically defined below:
 - Trigeminal neuropathic pain: failed peripheral injection, percutaneous RF ablation, transcutaneous stimulation, peripheral nerve stimulation, caudalis DREZ lesioning, trigeminal tractotomy, motor cortex stimulation, intraventricular or intrathecal medication infusions, or deep brain stimulation
 - Trigeminal deafferentation pain: pain has resulted from failed trigeminal procedures including percutaneous RF rhizotomy, percutaneous chemical rhizotomy, percutaneous balloon compression rhizotomy, stereotactic radiosurgery, microvascular decompression, or intracranial partial sensory rhizotomy
 - Postherpetic neuralgia of the trigeminal nerve: failed peripheral injection, percutaneous RF ablation, transcutaneous stimulation, peripheral nerve stimulation, caudalis DREZ lesioning, trigeminal tractotomy, motor cortex stimulation, intraventricular or intrathecal medication infusions, or deep brain stimulation
7. Central lateral nucleus of thalamus can be targeted by the ExAblate device. The CL region of the thalamus must be apparent on MRI such that indirect targeting can be performed by measurement from a line connecting the anterior and posterior commissures of the brain.
8. Able to communicate sensations during the focused ultrasound treatment

9. Stable prescribed doses of all symptomatic pain medications for 30 days prior to study entry and for the duration of the 3-month blinded phase of the study.
- 10.

5.3 Exclusion Criteria

1. Craniofacial pain syndromes related to malignancy of the head and neck
2. Idiopathic trigeminal neuralgia
3. Headache syndromes like migraine, cluster headache
4. Temporomandibular joint syndrome
5. Atypical facial pain or pain related to a somatoform disorder
6. Subjects deemed poor candidates by a licensed psychologist with expertise in screening for pain procedures as evidences by:
 - a. Significant clinician concern about reliability of subject-reported information, such as subject in active process of seeking disability for neuropathic pain
 - b. Subjects exhibiting any behavior(s) consistent with ethanol or substance abuse as defined by the criteria outlined in the DSM-V as manifested by one (or more) of the following occurring within a 12 month period: Recurrent substance use resulting in a failure to fulfill major role obligations at work, school, or home (such as repeated absences or poor work performance related to substance use; substance-related absences, suspensions, or expulsions from school; or neglect of children or household). Recurrent substance use in situations in which it is physically hazardous (such as driving an automobile or operating a machine when impaired by substance use)
 - c. Recurrent substance-related legal problems (such as arrests for substance related disorderly conduct)
 - d. Continued substance use despite having persistent or recurrent social or interpersonal problems caused or exacerbated by the effects of the substance (for example, arguments with spouse about consequences of intoxication and physical fights).
7. Subjects with active psychiatric illness will be excluded. For the purpose of this study, active psychiatric illness includes:
 - a. Exhibiting current suicide ideation and/or a history of suicide attempt within past 2 years
 - b. been hospitalized for the treatment of a psychiatric illness within the past 2 years
 - c. received transcranial magnetic stimulation for depression treatment
 - d. received electroconvulsive therapy for depression
8. Any presence or history of psychosis will be excluded.
9. Subjects with unstable cardiac status including:
 - a. Unstable angina pectoris on medication

- b. Subjects with documented myocardial infarction within six months of protocol entry
- c. Significant congestive heart failure defined with ejection fraction < 40
- d. Subjects with unstable ventricular arrhythmias
- e. Subjects with atrial arrhythmias that are not rate-controlled

10. Severe hypertension (diastolic BP > 100 on medication)

11. Subjects with standard contraindications for MR imaging such as non-MRI compatible implanted metallic devices including cardiac pacemakers, size limitations, etc.

12. On medications that increase the bleeding risk, we are following the published guidelines which are currently recognized by the American Society of Regional Anesthesia and Pain Medicine, American Academy of Pain Medicine and the North American Neuromodulation Society (Reg Anesth Pain Med 2015;40: 182–212); specifically:

- a. Aspirin or another antiplatelet medication (clopidogrel, prasugrel, ticlopidine, abciximab) for the last 7 days prior to treatment.
- b. Oral, subcutaneous or intravenous anticoagulant medications, such as oral vitamin K inhibitors for the last 7 days, non-vitamin K inhibitor oral anticoagulant (dabigatran, apixaban, rivaroxaban) for the last 72 hours.
- c. Intravenous or subcutaneous heparin-derived compounds for the last 48 hours.

13. Individuals who are not able or willing to tolerate the required prolonged stationary supine position during treatment (can be up to 4 hours of total table time.)

14. Subjects participating or have participated in another clinical trial in the last 30 days

15. Presence of systemic neurological disease or dysfunction

16. Known life-threatening systemic disease

17. Subjects with risk factors for intraoperative or postoperative bleeding from a documented coagulopathy or if their serum coagulation studies (platelet count, PT, PTT, and INR) exceed the institutional laboratory limits.

18. Subjects with brain tumors or any significant intracranial mass. *Trigeminal or cavernous sinus tumors causing neuropathic pain are not excluded.*

19. Any illness that in the investigator's opinion preclude participation in this study

20. Pregnancy or lactation

21. Legal incapacity or limited legal capacity

22. Subjects with a deep brain stimulation implant or with a prior stereotactic thalamic ablation

23. Skull density ratio, calculated from the baseline noncontrasted head CT, is less than 0.4

24. History of hemorrhagic stroke or cerebrovascular event within the past year of treatment exhibiting incomplete resolution

25. History of seizures within past year of treatment

26. Severe kidney disease or on dialysis

[figure not shown]
27. Subjects who are unable to tolerate medications due to intolerable side effects.
28. Subjects whose primary pain is other than craniofacial neuropathic pain.

6.0 INVESTIGATIONAL PLAN

6.1 Study Design

This study is designed as a prospective, double-blinded, randomized trial in 10 subjects with sham procedures serving as the control. A rigorous clinical trial design is required for the subjective measurement of pain and clinical outcome where a placebo effect is anticipated. Primary safety and efficacy assessments will be made before and after treatment through the 3 month blinded phase. After 3 months, subjects in the sham arm will be offered a focused ultrasound bilateral thalamotomy as an open label extension of the study. All subjects receiving treatment, either during the primary blinded analysis or open-label extension phase, will be followed for at least 3 months post-thalamotomy.

Neuropathic Pain Study Flow

6.2 Sham Study Design

The randomized, control arm subjects will undergo a sham procedure that is identical to the treatment except the energy output will be disabled. These control subjects will then be followed up for 3-months post-sham procedure to assess study endpoints; study follow-up: 1 day, 1 week, 1 and 3 month visits.

At the 3-Month time point, all subjects will be unblinded and offered crossover to the actual treatment. All these crossover subjects will be followed again according to the same schedule as the treatment through the Month 3 post treatment study visit.

6.3 Pre-Treatment Procedures

1. PRE-SCREENING: Subjects with medication-refractory, trigeminal or other craniofacial neuropathic pains may be eligible for the study. The diagnosis will be confirmed by the neurosurgeon from the patient's medical history and physical examination.
2. CONSENT: Those who meet the preliminary criteria for the study based on pre-screening of available information will be offered an Informed Consent to sign prior to further evaluation (see Appendix-B for an Informed Consent template). Those who accept will be assigned a subject study number. No study specific tests or procedures will be done until the subject has signed consent.
3. SCREENING and ENROLLMENT:
 - a. All current medications will be documented in the medical record and any changes over the past two months will be noted. Record prescribed and PRN medication usage.
 - b. The investigator will review and document any medical history that pertains to study eligibility.
 - c. Subjects will complete screening questionnaires
 - Worst 24 Hr NPRS assessment, including report of pain levels over past two months (for eligibility)
 - PROMIS (patient reported outcomes of pain)
 - a. Intensity
 - b. Neuropathic pain quality
 - c. Nocioceptive pain quality
 - d. Behavior
 - e. Interference
 - d. Focused neuro-exam by neurosurgeon including:
 - Cranial nerve examination
 - Sensory examination
 - Gait
 - e. Screening blood tests: Blood will be drawn by venipuncture for PT, PTT, Metabolic panel, and CBC including platelets
 - f. Women of childbearing age will undergo a urinary or serum Beta-hCG test for pregnancy. If the test is positive, the subject will be excluded from the study. If the test is negative, she must agree to maintain a suitable form of birth control throughout study. This includes the screening period until study completion.

g. A comprehensive assessment of pain symptoms, functional limitations, and comorbid mood issues will be made by licensed pain psychologist. The evaluation consists of a clinical interview, as well as questionnaires/assessment tools that address mood and identify potential biopsychosocial factors that may contribute to the patient's pain experience. The Patient Health Questionnaire (PHQ-9) identifies potential depressive symptoms and the Generalized Anxiety Disorder 7-Item Scale (GAD-7) addresses anxiety. Additionally, the Pain Catastrophizing Scale (PCS) is helpful in recognizing a patient's tendency toward catastrophic thinking that is likely to negatively impact surgical or other invasive interventions' outcomes. Lastly, the Brief Battery for Health Improvement 2 (BBHI-2) is a psychometrically sound instrument that is normed on patients with pain and provides objective information related to underlying pain-related issues that are biopsychosocially related. Standard screening for pain procedures includes assessments of anxiety and mood:

- GAD-7
- PHQ-9
- PCS
- BBHI-2

h. Evaluation by a pain management physician.

i. CT Imaging: For the purpose of this study, the CT Exam should be an Axial scan with bone filter, an image resolution of 512x512, and image thickness of 1mm with zero (0) spacing

j. MR Imaging: For the purpose of this study, unenhanced MR Exams will be performed and include: volumetric MPRAGE, axial and coronal T2-weighted sequences, and axial and coronal diffusion-tensor imaging (DTI)

k. Once all items required for eligibility are completed, the principal investigator will review and sign eligibility or document the screen-failure. If at this point it is determined that the subject **does not** meet all Inclusion and Exclusion criteria and cannot be treated, the subject will be removed from the study. These subjects will be considered screening failures, and will not be included in any of the safety or efficacy endpoint analyses.

l. If the subject is deemed eligible for the study based on the screening criteria, then the following will be scheduled:

- Presurgical evaluation by the anesthesiology team
- Baseline assessments including Dynamic FDG PET imaging using the following process
 - a. Placement of IV catheter

- b. Slow injection with ~10 mCi of the FDG tracer via the catheter
- c. Imaged using the PET/CT scanner for 60 minutes starting at injection
- d. The final 10-15 minutes of the 60 minute scan will consist of a static FDG PET scan.
- Procedure (sham or treatment).

4. BASELINE ASSESSMENTS:

During the week prior to the procedure, the subject will be provided with time to complete all questionnaires per the schedule of events. These will establish the baseline measures for these particular data points. Baseline assessments include:

- NPRS
- PROMIS measures of pain
- History and physical exam
- Concomitant medications
- Dynamic FDG PET

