6.7 Follow-up

Subject follow-up will be completed at Day 1, Day 7, Month 1, and Month 3 for all subjects who underwent CL lesioning/ablation using ExAblate system. Subject follow-up will be similar for those who underwent sham treatment. At 3 months, subjects who had sham treatment will be unblinded and offered MRgFUS.

Subjects will be evaluated at all follow-up visits for general health, neurological changes and efficacy measurements as well as for device/procedure related adverse events that may have occurred during the follow-up period. Medication regimen and PRN usage will be recorded at each follow-up along with the following assessments:

6.7.1 Day 1

- Evaluation of general health and neurological changes
- NPRS (Worst pain in 24 hrs)
- PROMIS
- Assess patient blind
- Assess safety and update adverse events as needed
- Review medications and record any changes
- MRI

6.7.2 Day 7

- Evaluation of general health and neurological changes
- NPRS (Worst pain in 24 hrs)
- PROMIS
- PGIC
- Assess patient blind
- Assess safety and update adverse events as needed
- Review medications and record any changes
- MRI

6.7.3 Month 1

- Evaluation of general health and neurological changes
- NPRS (Worst pain in 24 hrs)
- PROMIS
- PGIC
- Assess patient blind
- Assess safety and update adverse events as needed
- Review medications and record any changes
- MRI

6.7.4 Month 3

- Evaluation of general health and neurological changes
- NPRS (Worst pain in 24 hrs)
- PROMIS
- PGIC
- Assess patient blind
- Neuropsychological Pain Assessment
- GAD-7
- PHQ-9
- PCS
- BBHI-2
- MRI

- Dynamic FDG PET
- Assess safety and update adverse events as needed
- Review medications and record any changes
- Evaluation by a pain management physician

All pre-treatment and post treatment MR images will be de-personified (i.e.: subject identifiers made anonymous), archived and sent to InSightec. These analyses will also include full radiological assessments from baseline through all follow up visits.

In this study, subjects who use alternative treatments (not including medication change) during the 3-month follow-up period will be exited from the study, after completing required study examinations. The reason(s) for study exit will be noted on the Case Report Forms.

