7.0 STUDY REQUIREMENTS AND VISIT SCHEDULE

The table below summarizes the study visit schedule and procedures.

Procedures	Screening	Baseline (within 1 week of day 0)	Day 0 (Proced- ure)	Day 1	Day 7 (±3 days)	Months 1 (±7 days)	Month 3 (±14 days) ¹
Written Consent	X						
Check Eligibility	X						
Demographics	X						
History and Physical Exam		X					
Screening Labs	X						
CT Scan	X						
MRI	X			X	X	X	X
Dynamic PET		X					X
NPRS and PROMIS Pain Questionnaires ²	X	X		X	X	X	X
PGIC					X	X	X
Neurological Exam	X			X	X	X	X
Pain Psychological Exam ³	X						X
Pain Management Exam	X						X
MRgFUS Treatment or Sham Procedure			X				
Assessment of patient blind			X	X	X	X	X
Concomitant Medications (prescribed and PRN)	X	X	X	X	X	X	X
Adverse Events			X	X	X	X	X

¹ Subjects will be un-blinded to randomization arm at the completion of month 3 visit. Subjects who initially were randomized to the sham arm may go back to day 0 in schedule of events and receive an unblinded MRgFUS thalamotomy.

² Five PROMIS fixed length short forms to be completed on paper at each indicated timepoint. PROMIS scale v1.0: Pain Intensity 3a, Pain Behavior 7a, Pain Interference 8a. PROMIS scale v2.0: Neuropathic Pain Quality 5a, Nociceptive Pain Quality 5a.

³ To include: GAD-7, PHQ-9, PCS, BBHI-2

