9.1 General Device Related Risks

Risk of Magnetic Resonance Scanners:

MRI has no known deleterious biological effects in subjects with no contraindications. The incidence of claustrophobia during MRI examinations is approximately 10-15%, although it is expected to be less frequent in the study population due to the use of sedation.

Risk of Intravenous (IV) Catheter:

There is a potential risk from the IV catheter used during the ablation. Participants can expect a small amount of pain and/or bleeding/bruising at the IV site. There is a small risk of infection. This procedure will follow the ‘standard of care’ at the study sites.

Risks related to Dynamic FDG PET imaging:

PET Scan: This imaging study involves radiation exposure from a Positron Emission Tomography (PET) scan combined with a Computed Tomography (CT) scan using the radiopharmaceutical F-18 FDG. Using the standard way of describing radiation dose, from participating in this study, the wall of your bladder, heart, and pancreas will receive the most radiation from this study. All other organs will receive smaller amounts of radiation. Although each organ will receive a different dose, the total effective radiation dose you will receive from one procedure is approximately 10 mSv. You will have 2 of these scans. For comparison, this dose is roughly 40% the annual radiation dose safely allowed for a radiation worker such as the person performing your scan.

This radiation exposure is not necessary for your medical care but is necessary to obtain the research information desired. This radiation dose is what you will receive from this study only and does not include any exposure you may have received or will receive from other tests. If you

are pregnant or breastfeeding, you may not participate in this research study. It is best to avoid radiation exposure to unborn or nursing children since they are more sensitive to radiation than adults.

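### Pregnancy is tested only at Screening, although the research-only FDG PET is repeated at Month 3; a urine test before that scan is a cheap, low-priority safety improvement

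*Protocol*

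**What the plan says.** Protocol 6.3, item 3f, under screening and enrollment: "Women of childbearing age will undergo a urinary or serum Beta-hCG test for pregnancy". A positive result excludes the subject. After a negative result, "she must agree to maintain a suitable form of birth control throughout study", from the screening period to the end of the study. Exclusion 20 in section 5.3 reads "Pregnancy or lactation".

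The dynamic FDG PET is done at Baseline and at Month 3 (sections 3.2, 6.3, 6.7.4 and 7.0). The Month 3 visit has a window of 14 days either side. Section 9.1 puts each scan at about 10 mSv effective dose and says that the exposure serves the research and not the subject's care. It bars pregnant and breastfeeding women from the study because unborn and nursing children are more sensitive to radiation. On the number of scans it says "You will have 2 of these scans".

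Each follow-up visit in section 6.7 includes "Evaluation of general health and neurological changes", together with adverse-event and medication review.

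For sham subjects who cross over, section 7.0 (footnote 1) says they "may go back to day 0 in schedule of events and receive an unblinded MRgFUS thalamotomy". Section 6.2 says they are "followed again according to the same schedule as the treatment through the Month 3 post treatment study visit".

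**The concern.** Section 9.1 makes not being pregnant a condition for the radiation exposure. The protocol checks that condition by test once, before the first scan. The second, identical scan comes months later, and no test precedes it. By then the subject's status rests on her agreement to use birth control and on what she knows and reports at visits.

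At stake is patient safety only. If contraception fails and the pregnancy is not yet recognised at Month 3, the woman receives a PET/CT that brings her no medical benefit and that the protocol does not want pregnant women to have. Pregnancy testing and the visit schedule belong in the protocol, so this is not a matter that a statistical analysis plan would settle.

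**Working it through.** **1. Where a test could appear in the Protocol**

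- 6.3 item 3f (Screening): beta-hCG test. This is the only one.
- 6.3 item 3l (steps of the PET procedure): no pregnancy check before injection.
- 6.3 item 4 (Baseline, within one week of Day 0): history and physical exam, no test.
- 6.5 (treatment day): none.
- 6.7.1 to 6.7.4 (Day 1 to Month 3): clinical reviews, no test.
- 7.0 schedule: no pregnancy-test row; screening labs are marked at Screening only.

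**2. Earliest Month 3 PET after Day 0**

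The formula is three months minus the 14-day window. The protocol does not define a month, so the range is:

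- 28-day months: 84 − 14 = 70 days
- 30-day months: 90 − 14 = 76 days
- average months of 30.44 days: 91.3 − 14 = 77.3 days
- calendar months (89 to 92 days): 75 to 78 days

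The time since the test itself is longer, because Screening precedes Baseline and section 7.0 sets no maximum interval from Screening to Day 0.

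**3. Chance of an unrecognised pregnancy at the Month 3 PET, per woman concerned**

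Neither input is in the protocol; both are assumptions. Let p be the yearly contraception failure (1% or 10%) and w the time for which a pregnancy stays unrecognised (28 or 42 days). Then the chance is 1 − (1 − p)^(w/365):

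- p = 1%, w = 28: 1 − 0.99^(28/365) = 0.077%
- p = 1%, w = 42: 1 − 0.99^(42/365) = 0.116%
- p = 10%, w = 28: 1 − 0.90^(28/365) = 0.805%
- p = 10%, w = 42: 1 − 0.90^(42/365) = 1.205%

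Because w is below 70 days in every case, the result depends neither on the exact day of the scan nor on the Screening interval. The 70 to 78 days show only that the Screening test cannot speak for this scan.

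Ceiling for the whole trial, if all ten subjects were women concerned: 10 × 0.077% = 0.008 to 10 × 1.205% = 0.12 expected cases. Men and women aged 18 to 75 are eligible, so the true figure is probably lower and may be zero.

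**4. What a urine test would leave undetected**

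Assume that a test is negative for the first 10 to 14 days after conception. The share of the window that is missed then runs from 10/42 = 24% to 14/28 = 50%. The test reduces the risk but does not remove it.

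**5. Crossover**

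Sham subjects re-enter at Day 0, not at Screening, so item 3f is not repeated. Repeating the same schedule (6.2) would imply another Month 3 PET; the count of two scans (9.1) would not. The text does not settle which is meant.

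**The case against.** The strongest case against is that the protocol made a defensible choice: one test, exclusion on a positive result, mandatory birth control to the end of the study, and an explicit radiation bar. Other contacts add protection: the Baseline history and physical exam, the presurgical anesthesiology evaluation, adverse-event and medication review at every follow-up visit, and a pain physician's evaluation at Month 3. The consent form is not shown and may ask women to report a possible pregnancy; a PET unit may also have its own routine. The probability rests wholly on assumed inputs, in a descriptive study of ten subjects.

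Most of this stands, and it sets the priority. It does not close the gap. The listed contacts can bring out a pregnancy that the woman knows of or suspects, but none is stated to include a test, and an evaluation before Day 0 says nothing about Month 3. What unseen documents or local routine might add cannot be credited.

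A reader might infer more than the text supports:

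- **That the pregnancy texts contradict each other.** They do not. Exclusion 20, item 3f and section 9.1 agree; what is missing is a later check.
- **That the crossover thalamotomy without a retest is a comparable hazard.** The protocol names no fetal hazard of the thalamotomy. Its stated concern for unborn children is radiation.
- **That the long gap makes the risk large.** The gap does not enter the calculated probability.

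**Conclusion.** The point holds as a modest safety improvement. Pregnancy is tested once, and the protocol's own condition for a research-only exposure of about 10 mSv is not re-checked by test before the Month 3 scan. The Baseline scan is a lesser case, since the Screening test may be old by then.

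The size is about 0.1% to 1.2% per woman concerned, under the assumed failure rate and unrecognised window. The number of such women is not stated and may be zero. The protocol gives no fetal dose, so the harm itself cannot be sized. No effect estimate, error rate or analysis set is touched. It is worth doing because it costs almost nothing, but the priority is low.

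**What to change.** - Add to 6.7.4 and to the 7.0 schedule a urine beta-hCG test for women of childbearing age, shortly before tracer injection at the Month 3 PET.
- Require the same before the Baseline PET if the Screening test is not recent (for example, more than 7 days old), and before any PET repeated after crossover.
- State that a positive test after randomization omits the PET, while follow-up continues and all other data are kept.
- Amend 9.1 and item 3f to match, so that the bar on pregnant women refers to enrolment and to PET exposure. Otherwise the new rule would conflict with the present bar on taking part.
- Optional: a retest before the crossover Day 0, to re-check exclusion 20.

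The cost is one schedule row, a few sentences and a few urine tests. The downside is a possible missing Month 3 PET value, which is a secondary outcome.
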